Consent will be obtained from an individual and their household members at time of enrollment by study staff only after a full explanation has been given, and time allowed for consideration and questions. This process will mainly occur over the phone with individuals consenting via REDCap questionnaires. Though for families unable or not willing to consent via REDCap, and in-person consent visit with the study team can be scheduled. Individuals under 18 years of age will have consent provided by their parent or legal guardian. In addition to consent by their legal guardian, study staff will attempt to obtain assent from individuals 7 to 18 years of age when applicable. Following the consent process, all household members will receive a paper or electronic copy of the consent form.

All subjects who consent to participate will also be asked to approve the storage of their biospecimens (nasal swabs). Persons who consent to the study, but who do not want their biospecimens stored may still participate in the study. Their biospecimens will be tested as per protocol, but the remaining aliquots will be destroyed once test results of sufficient quality are reported.

Study Personnel

Given the scale of this project and the necessity to collect data of the highest quality, an extensive organizational structure is necessary to ensure that adequate supervision is provided at all levels of organization. For this study, the organizational structure will fall into five categories:

- **Enrollment and Follow-up team:** This team will be responsible for completing the screening and obtaining consent from all study participants. This team will be comprised of study staff who will be directly supervised by the research lead team. All members of the enrollment team will receive extensive training in the specifics of this protocol prior to the start of participant enrollment. Members of this group will be responsible creating the participant trainings (excluding the Ellume home-testing video) for this study. Additionally, members of this group will be responsible for going to the households when in-person training is requested. This team will also be responsible for sending the weekly reminders to households (see Weekly Monitoring section), and reviewing adverse event questionnaires to determine whether there is evidence of short-term reaction to the study drug.

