All sick individuals, meaning those drug eligible and those drug ineligible, will complete an illness questionnaire in REDCap 7 days after they report the illness. This questionnaire will collect information on the presence or absence of respiratory and systemic symptoms during the 7 days after reporting the illness. Data will also be collected on childcare, school, and work absenteeism, and subsequent visits to health care providers. Additionally, the influenza-diagnosed individual will provide nasal swab specimens collected via self-swab or parent/legal guardian-swab at Study day 2-3 and Study day 5-7. These swabs will be returned to the laboratory via a delivery services the day of or the day after collection (See VI. Laboratory Procedures section). In addition to the illness questionnaire, the drug eligible, influenza infected participant will complete a standard questionnaire at 7 and 14 days following study drug receipt to monitor for the occurrence of adverse events (AEs) or serious adverse events (SAEs). These questionnaires will be monitored by a member of the study team. Additionally, any provider consultations with tele-health following drug administration will be reported to the study team to monitor for the occurrence of adverse events (AEs) or (SAEs). Any reported adverse events will be assessed to determine if related to drug treatment and whether unexpected or not and subsequently reported to the IRB using a standardized AE and SAE form. After the self-collected nasal swabs have been tested in the laboratory, the case will have to ability to view the results of their swab on the Seattle Flu Study website.

For all individuals that provide nasal swab specimens for testing and further characterization, they will have the ability to view whether influenza or respiratory syncytial virus (RSV) was detected from their swab(s) on the Seattle Flu Study website (See VI. Laboratory Procedures).

Data collection

Data will be collected electronically in REDCap online via a computer or mobile device or through a text-message accessible app. The major data collection activities will occur at the following times (See Table 1).

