Serious Adverse Events: Serious adverse events (SAEs) under Good Clinical Practice (GCP) guidelines include death, a life-threatening reaction to the study drug (or placebo) or other study procedure, hospitalization, or significant or persistent disability or impairment. Other events may also be considered a serious adverse event if, based on medical judgement, the event jeopardized the patient to the point of requiring medical or surgical intervention to

Other Adverse Events: This will include any untoward medical event that occurs in a participant, any unfavorable sign or symptom temporally associated with the provision of the intervention, or any noxious or unintended response to the study drug. These other adverse events can be anticipated based on what we know about reactions to antiviral medications, or unanticipated. Examples of anticipated adverse events include (but are not limited to) instances of nausea, headache, or diarrhea.

Unanticipated adverse events are those that are either unexpected in terms of nature, severity, and frequency especially if they indicate that there is greater risk of harm than previously recognized.

Within 48 hours of taking the study drug, cases will be screened via REDCap for evidence of short-term reaction. Additionally, drug eligible, influenza-positive study participants will be

monitored at 7 and 14 days after receipt of the intervention using a standardized questionnaire. Any potential AE or SAE based on post-drug tele-health consultation will be reported to the study team as soon as possible, which will be entered into the standardized questionnaire. These questionnaires will be monitored by the data management team, such that adverse events will be reported as soon as possible. All SAEs (regardless of causality), and any grade 3 and 4 AEs which are deemed related or possibly related to the study drug, will be logged in AE database and reported using an official Adverse Event Report Form to the designated principal investigator ([name]) for review within 48 hours. This review will determine if there is any indication for the event being related to the study intervention or procedures. The medical expert team will review the file and make a determination regarding attribution to study procedures or the intervention.

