If the adverse event is considered by the medical expert team to be minor in severity, it will be logged in the centralized data capture system and a summary of such events will be reported to the DSMB. If the severity of the adverse event is considered to be moderate or severe by Principal and Co-Principal Investigators, it should be reported to the safety officer (DSMB) and the cognizant IRB immediately. All study-related SAEs will be reported to the IRB within 14 days.

The following are a list of anticipated and unanticipated adverse events we expect to be attributable to the study procedures or the intervention:

Anticipated Events: Mild-moderate systemic reactions, these include diarrhea, bronchitis, nausea, nasopharyngitis, and headache.

Unanticipated Events: By definition these are unexpected in terms of their nature, (see above for anticipated events) severity, and frequency, especially if they indicate that there may be greater risk of harm than previously recognized.

X. Definitions

Acute Respiratory Illness/infection (ARI): We will use the CDC definition of ARI that includes disease that typically involves the airways within the nose and throat and may or may not include fever. ARI is generally defined by the presence of two or more symptoms such as fever, cough, runny nose or nasal congestion, or sore throat. ARI is more sensitive (broader) than ILI to describe illness consistent with influenza because fever/feverishness are not required.

Drug eligible, influenza-infected study participant: A drug eligible study participant in the household that is diagnosed with influenza from a 98point6 provider based on a clinical review of the sick participant's symptoms.

Drug ineligible participant: A study participant in the household that is not able to receive BXM.

Influenza-like Illness in Adults and Adolescents (ILI): We will use the CDC definition of ILI that requires reported or measured fever ($>37.8^{\circ}\text{C}$) plus either cough or sore throat on one or more days preceding consultation with a tele-health physician.

Laboratory-confirmed influenza infection: We will use the CDC definition that is an individual who tests positive for influenza via an approved laboratory test, which will be the multiplex PCR (Cepheid) in this study.

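### Protocol section IX makes relatedness both the entry condition and the result of medical review for non-serious grade 3-4 adverse events, names no one for the first judgement, and conflicts with the protocol's other reporting rules

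*Protocol*

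**What the plan says.** **The gate.** In Protocol IX, under the plan for reporting unanticipated problems and adverse events, serious events are forwarded without a causality test (the rule opens "All SAEs (regardless of causality" and closes the bracket there). For other events the rule is that "any grade 3 and 4 AEs which are deemed related or possibly related to the study drug, will be logged in AE database" and reported on a form to the designated principal investigator within 48 hours.

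**What the review decides.** The same paragraph continues: "This review will determine if there is any indication for the event being related to the study intervention or procedures". It then gives attribution to the medical expert team.

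**Who reads the questionnaires.** Protocol IX: "These questionnaires will be monitored by the data management team, such that adverse events will be reported as soon as possible". Protocol V, Study Personnel, gives the enrollment and follow-up team the task of "reviewing adverse event questionnaires to determine whether there is evidence of short-term reaction to the study drug". Protocol V, Follow-up, leaves it to an unspecified team member.

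**Other routes.** Protocol V, Follow-up: "Any reported adverse events will be assessed to determine if related to drug treatment and whether unexpected or not", after which they are reported to the IRB. The later paragraph of Protocol IX routes by severity. Events that the medical expert team considers minor are logged and summarised to the DSMB. "If the severity of the adverse event is considered to be moderate or severe by Principal and Co-Principal Investigators", the event goes at once to the safety officer and the IRB. Neither route carries a causality condition.

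**The concern.** A review cannot be entered on the strength of its own conclusion. Someone must decide that a grade 3-4 event is at least possibly related before the clinicians who are meant to decide this have seen it, and the protocol does not say who.

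This matters more here than in many trials. Everyone given baloxavir is being treated for probable influenza, so a severe symptom after dosing has an obvious alternative explanation. If the first reader accepts it, the gate in section IX requires neither an entry in the adverse event database nor a report to the principal investigator. The SAP does not catch such events later: its Safety Analysis section covers serious adverse events and baloxavir-resistant influenza, with no analysis of non-serious grade 3-4 events. What is at stake is the completeness of the safety record for the study drug.

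**Working it through.** No sample size, error rate or event count bears on this, so the check is to set the texts side by side and follow one event through them.

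**Inputs**

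- Gate on non-serious grade 3-4 events: related or possibly related (Protocol IX). Assessor: not named.
- Gate on serious events: none (Protocol IX).
- Attribution: medical expert team, after the report is filed (Protocol IX). This team is the research nurse, the principal and co-principal investigators and the Safety Officer (Protocol V, Study Personnel).
- First reader: data management team (IX), enrollment and follow-up team (V, Study Personnel), or an unspecified member (V, Follow-up). The data management team's stated qualification is data management experience. The enrollment team's is protocol training. No clinical qualification is stated for any of the three.

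**Tracing three kinds of event**

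1. *Serious event.* It goes to the principal investigator whatever its cause. No gap.
2. *Non-serious grade 3-4 event that the first reader thinks possibly related.* It is logged, reported within 48 hours and attributed by the medical expert team. No gap.
3. *Non-serious grade 3-4 event that the first reader puts down to influenza.*
   - Under the gate in IX: neither the database entry nor the report to the principal investigator is required.
   - Under V, Follow-up: it must be assessed for relatedness and reported to the IRB. No assessor is named.
   - Under the severity paragraph in IX: it goes to the safety officer and the IRB at once, but only after the investigators have judged its severity, so they must already have it. The gate does not bring it to them.
   - Under the short-term reaction rule in V, Follow-up: a medical expert is consulted once there is evidence of a drug reaction, which is the same unassigned judgement.

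The third event therefore has different outcomes under different paragraphs, and no text says which one governs.

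**A second inconsistency.** V, Follow-up sends every assessed event to the IRB. The severity paragraph in IX has minor events only logged and summarised to the DSMB. Both cannot hold for a minor event.

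**Scale of the pilot.** Protocol XI expects 250 × 0.25 = 62.5, rounded to 63, confirmed infections. Protocol II stops further baloxavir deliveries to a household once one member has received it, so at most one person per household is treated. Treatment follows a tele-health diagnosis, not laboratory confirmation, so 63 is only a guide to the number treated. The documents give no grade 3-4 event rate, so the number of events at risk cannot be computed.

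**The case against.** The best defence is that the gate governs only an expedited form. On that reading V, Follow-up still has every reported event assessed and sent to the IRB, and the severity paragraph in IX presumes that the medical expert team sees even minor events. The gate also includes possibly related events, which is wide, and it exempts serious events. Section IX does not say that data managers judge causality; the only team it names for attribution is clinical. Tele-health providers are a further clinical source of reports. The two named reading teams may cover different forms, since Study Personnel speaks of short-term reactions while the sentence in IX follows the 7- and 14-day monitoring. A Manual of Operations, which is not among the documents, may settle the detail.

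Much of this stands, and it limits the point. A reader might infer that severe events will escape clinicians and the IRB. The documents do not show that, because the ungated texts point the other way. Nor do they say that non-clinical staff make the causality call; they leave it unassigned. But the expedited-form reading is not stated, and the defence relies on texts that conflict with the gate. It confirms that the protocol needs reconciling.

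Two other inferences should be resisted. Diarrhea, nausea and headache appear both among the anticipated reactions and in the symptom table of Protocol II, but section IX calls the anticipated reactions mild to moderate, so the overlap does not measure what is lost at grade 3-4. And "All study-related SAEs will be reported to the IRB within 14 days" is not shown to contradict the immediate-report rule: one concerns seriousness and the other severity, and an immediate report meets a 14-day limit.

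**Conclusion.** The point holds as a circular rule with an unnamed assessor, in conflict with two other reporting texts. It is confined to non-serious grade 3-4 events; serious events are protected. For an event of this kind put down to influenza, logging and review depend on which paragraph staff follow. A miss is possible under the wording but not demonstrated, and neither its frequency nor any resulting bias can be estimated from the documents.

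The conclusion assumes that no procedure outside these documents names the assessor or ranks the paragraphs. That the first readers lack clinical training is inferred from the team descriptions, and mistaking a reaction for influenza is a plausible scenario, not something that the documents state. The change is worth making because it is cheap and alters which events are recorded and reviewed.

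**What to change.** - In Protocol IX, extend to grade 3-4 events the rule that already applies to serious ones: log all of them regardless of causality and send them for review within the existing 48 hours. State that only the medical expert team assigns causality.
- Name one first reader of the adverse event questionnaires, so that V (Study Personnel), V (Follow-up) and IX agree. If different forms have different readers, say so.
- Reconcile V (Follow-up) with the severity paragraph in IX on which events go to the IRB and when, minor events included.

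The cost is protocol wording, an adjusted alert rule in REDCap, and a few more event forms for an existing team in a small single-dose pilot. No new staff are needed. It is not necessary to forward every moderate event within 48 hours: in people being treated for influenza that would sweep in ordinary symptoms of the illness, and it is a debatable trade-off.

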review the participant’s medical information and provide an influenza diagnosis based on clinical judgement. If probable influenza is diagnosed, the 98point6 provider will confirm that antiviral treatment is appropriate. If appropriate, drug eligible study participant will subsequently receive a single dose of BXM delivered to their household via rapid delivery service for therapy initiation within 48 hours of symptom onset. Concurrently, the ill individual will collect a Study Day 0 nasal swab sample that will be mailed back to the laboratory for further testing. Additional nasal swabs will be collected at Study Day 2-3 and Study Day 5-7. If influenza is not diagnosed, the ill individual will provide one self-collected or parent/permanent legal guardian-collected nasal swab specimen that will be mailed back to the laboratory for further testing, and the household will remain enrolled and all study participants in the household will continue to self-monitor for presence of symptoms. Once an eligible study participant receives BXM, no additional household members will be eligible to receive BXM; the household will be able to continue monitoring for onset of symptoms, as well as self-testing and swabbing when symptoms develops, but the household will no longer be able to receive BXM delivery.

Figure 1. Study schema

Symptom Table

Feeling Feverish	Muscle or Body Aches
Headache	Rash
Sore Throat or Itchy/Scratchy Nose	Runny/stuffy nose
Feeling More Tired Than Usual	Muscle or body aches
Nausea or Vomiting	Increased trouble with breathing
Ear Pain or Ear Discharge	Diarrhea

The study is being conducted in the Seattle, WA area over one influenza season. The goal is to have 250 households comply with full study procedures. Of these, 25% are estimated to have an individual in the household diagnosed with influenza based on estimates from previous household studies.^{23, 28-29}

A table for influenza attack rates by household size is provided below.

Household attack rate	Total households enrolled	Primary cases	Secondary cases (mean household size 5)	Secondary cases (mean household size 4)	Secondary cases (mean household size 3)
25%	250	63	45-96	34-72	23-48
20%	250	50	36-76	27-57	18-38
10%	250	25	18-38	14-29	9-19
Mean household size includes case.					
Secondary attack rate 18-38%, secondary cases presented as a range based on these high and low bounds. ³⁰⁻³²					

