The University of Washington is the sponsor of the study which is supported by an anonymous funder who does not have any ownership over the management and conduct of the study, the data, or the rights to publish.

III. Objectives

The objective of the study is to measure the proportion of individuals who are initiated on antiviral therapy within 48 hours of symptom onset using a home-based self-test, followed by a telehealth consultation to diagnose influenza and home delivery of antivirals

Primary Outcome Measures

The primary outcome measure will be the proportion of eligible individuals who initiate antiviral therapy at home within 48 hours of symptom onset utilizing a home-based test and the telehealth app for influenza diagnosis and rapid home-delivery of antivirals. It will be calculated using binomial regression with log link, where the number of drug eligible influenza-diagnosed individuals, defined as the number of individuals eligible to receive BXM with both self-test positive influenza and laboratory-confirmed influenza, reporting administration of the study drug within 48 hours of symptom onset is divided by the total number of drug eligible individuals with both self-test positive influenza and laboratory-confirmed influenza.

Secondary endpoints:

- Proportion of individuals who test positive for influenza using the home-based test within 48 hours of symptom onset
- Proportion of individuals with a positive home-based influenza self-test who have a positive test confirmed by the central laboratory
- Sensitivity and specificity of a self-test compared to a laboratory-based molecular influenza test
- Proportion of individuals who are delivered antivirals within 48 hours of symptom onset
- Proportion of individuals who self-report administration antiviral therapy within 48 hours of symptom onset
- Symptom duration and severity among drug eligible and drug ineligible influenza-positive individuals
- Proportion of families with influenza infection diagnosed within 7 days of an index case (another influenza-positive household member)
- Viral quantity and duration of viral RNA detection among drug eligible and drug ineligible influenza-positive participants
- Proportion of drug ineligible study participants seeking medical care for respiratory illness symptoms
- Proportion of individuals who choose to take a self-test among those who are eligible to take a self-test

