Person-to-person transmission: We will use the CDC definition for influenza transmission that refers to the ability of an influenza virus to spread from one person to another, most commonly through large or small droplets containing influenza virus that are expelled when a sick person is coughing or sneezing.

XI. Statistical Analyses

The primary objective is to precisely estimate the proportion of drug eligible individuals with an influenza diagnosis who initiate treatment within 48 hours. We define precision in terms of the width of a 95% confidence interval. The width of a 95% CI will be less than or equal to $\pm 1.96 \cdot 0.5/\sqrt{n}$ where n is the number of individuals who test positive for flu. With 250 households participating and an attack rate of 25% we expect 63 individuals with confirmed influenza infection. This will give a 95% CI for the proportion initiating treatment of ± 0.12 or less.

The proportion of drug eligible individuals receiving the drug and initiating treatment within 48 hours of symptom onset using home-based self-test and delivery methods will be estimated. Binomial regression with log link will be used to calculate the relative risk of receiving and initiating treatment within 48 hours by demographic and clinical factors, including age, sex, race/ethnicity, symptom types, symptom severity, and duration of symptoms. The RR, 95% confidence intervals and p-values will be reported.

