For the secondary endpoints of symptom duration and severity, drug eligible and drug ineligible participants will be analyzed separately. Symptom severity will be measured on a 4-point scale (0 = no symptoms, 1 = mild, 2 = moderate, 3 = severe) for each influenza-associated symptom the participant reports experiencing. Influenza-associated symptoms the participant does not report as experiencing will be coded as 0. An additional analysis will be conducted comparing secondary endpoints for drug eligible, influenza-infected study participants that received and initiated treatment within 48 hours of symptom onset and those that initiated treatment later than 48 hours. Kaplan-Meier curves will be used to present and analyze time to resolution of symptoms, defined as the time when the influenza-positive participant reports experiencing no respiratory or systemic symptoms. For study participants who received BXM, a Cox proportional hazards model will be used to calculate the hazard ratio, 95% confidence interval, and p-value for symptom duration by group (therapy within 48 hours of symptom onset, and therapy after 48 hours of symptom onset). The analysis of drug ineligible study participants will use a similar approach but will cluster by household and use a robust variance for computing confidence intervals and p-values. For BXM recipients, symptom severity will be compared between groups (therapy within 48 hours of symptom onset, and therapy after 48 hours of symptom onset) using proportions for categorical measures of severity and Pearson's chi-square test, as well as using ordinal regression. As above, the analysis using ordinal regression of drug ineligible study participants will cluster by household and use a robust variance for computing confidence intervals and p-values.

For the secondary endpoints of maximum viral titer and duration of viral RNA detection, we will use t-tests or nonparametric alternatives and linear regression to assess maximum viral titer and Kaplan-Meier curves and Cox proportional hazards models to assess duration of viral RNA detection.

Interim Analysis

This study is being conducted over the course of one influenza season. Therefore, an interim analysis will not be performed.

Antiviral resistance analysis

The secondary outcome data regarding emergence of BXM resistance will be reviewed at the end of the influenza season via genome sequencing of the viral RNA.

Health economic analysis

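### The label influenza-infected rests on a provider's symptom review, so the early-versus-late symptom and viral comparisons could include PCR-negative people

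*Protocol*

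**What the plan says.** **The label.** Protocol Section X defines a drug-eligible, influenza-infected participant as one "diagnosed with influenza from a 98point6 provider based on a clinical review" of symptoms. Section II agrees: the provider is to "provide an influenza diagnosis based on clinical judgement". Section X separately defines laboratory-confirmed infection as "an individual who tests positive for influenza via an approved laboratory test, which will be the multiplex PCR (Cepheid) in this study", and does not link the two definitions.

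**Where the label, or the same gateway, selects an analysis set.**
- Section XI plans an additional analysis "comparing secondary endpoints for drug eligible, influenza-infected study participants that received and initiated treatment within 48 hours" of onset against those who started later.
- The second secondary hypothesis in Section III, on duration of viral RNA detection, uses the label for both timing groups.
- In Section XI the Cox model for symptom duration and the severity tests use everyone who received baloxavir (BXM). The health economic analysis uses everyone who started therapy.

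**Where another term is used.** The secondary endpoint list in Section III, the Kaplan-Meier sentence in Section XI and SAP objective S4 refer to influenza-positive participants or cases. Section X does not define that term. The viral paragraph of Section XI names no set.

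**The primary set.** Section III counts timely starters "divided by the total number of drug eligible individuals with both self-test positive influenza and laboratory-confirmed influenza". Section XI describes the "proportion of drug eligible individuals with an influenza diagnosis who initiate treatment within 48 hours", and gives the precision formula "where n is the number of individuals who test positive for flu". SAP Section B6 puts timely starters with cough and a positive self-test over all participants who were influenza-free at baseline.

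**The concern.** An operational label, which decides who is sent drug and follow-up swabs, is also used to choose who is analysed. It cannot be read as PCR-confirmed. The medication section of the protocol has influenza-infected participants receiving drug within 2-6 hours of diagnosis, while the swab for PCR is still to be mailed to the laboratory.

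Someone whose illness is not influenza has no influenza RNA to clear and no influenza for an antiviral to shorten. Including such people in a comparison of early with late treatment weakens any real difference. If their share differs between the timing groups, it can also create a difference that treatment timing did not cause. With several labels in play and no rule linking them, the analyst would have to choose the set after the data are in.

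**Working it through.** **1. The plan's own figure.** Inputs from Protocol Section XI: 250 households, attack rate 25%, half-width 1.96 × 0.5/√n.
- Cases: 250 × 0.25 = 62.5, given as 63.
- Half-width: 1.96 × 0.5/√63 = 0.1235, given as 0.12.

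Both reproduce. The 63 are described as confirmed infections, so the precision statement is about test-positive people and not provider diagnoses.

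**2. Dilution of a mean difference.** Let μ₁ and μ₀ be the mean outcomes of infected early and late starters, and ν the mean in uninfected people, taken as unaffected by timing. With infected share p in both groups:

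[pμ₁ + (1 − p)ν] − [pμ₀ + (1 − p)ν] = p(μ₁ − μ₀).

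At unchanged variance, the sample needed to detect the difference grows by 1/p². The documents give no value for p, so a wide range is assumed. The last column borrows 63 as the number of provider-diagnosed people, for illustration only.

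| Assumed p | Share of true difference kept | Sample multiplier 1/p² | Infected among 63 (63p) |
|---|---|---|---|
| 0.3 | 0.3 | 11.1 | 18.9 |
| 0.5 | 0.5 | 4.0 | 31.5 |
| 0.7 | 0.7 | 2.0 | 44.1 |
| 0.9 | 0.9 | 1.2 | 56.7 |

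**3. Unequal shares.** Suppose timing has no effect (μ₁ = μ₀ = μ) but the infected shares are p₁ in early and p₀ in late starters. The expected difference is (p₁ − p₀)(μ − ν). For RNA duration ν = 0. With p₁ = 0.7 and p₀ = 0.5 the difference is 0.2μ, and early treatment appears to prolong shedding. With the shares reversed it appears to shorten it. The direction cannot be predicted from the documents.

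**4. Can a PCR-confirmed set be formed?** Yes. Table 1 of the protocol plans a day 0 swab for all three groups of ill participants, and Section VI sends specimens for Cepheid PCR. The day 2-3 and day 5-7 swabs, however, are planned only for drug-eligible people with a provider diagnosis.

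**5. The primary set.** Section III requires two positive results. If the 63 are laboratory-confirmed and the self-test detects 50% to 90% of them (assumed), the set is 63 × 0.5 = 31.5 to 63 × 0.9 = 56.7 people. The half-widths are 1.96 × 0.5/√31.5 = 0.175 and 1.96 × 0.5/√56.7 = 0.130.

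The SAP's ratio is a different quantity. Assume mean household sizes of 3 to 5, as in the protocol's attack-rate table, with every member enrolled and influenza-free at baseline. The denominator is then 250 × 3 = 750 to 250 × 5 = 1,250. Even if all 63 cases started in time, the result would be 63/750 = 8.4% to 63/1,250 = 5.0%, where the Section III definition would give 100%.

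**The case against.** Several stronger readings are tempting, and the documents do not support them.

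- *That the viral and symptom analyses would certainly include uninfected people.* The endpoint list, the Kaplan-Meier sentence and SAP objective S4 all say influenza-positive. The text conflicts with itself, so the supportable wording is that they could.
- *That the Section X definition drives every secondary analysis.* It does not. The Cox, severity and cost sets are defined by receiving or starting the drug. PCR-negative people reach them through the provider diagnosis that precedes a prescription, so rewording Section X alone would leave those sets unchanged.
- *That the cost comparison is wrong.* Costing everyone treated is a defensible way to evaluate a strategy of treating on clinical judgement, since treating uninfected people also costs money.
- *That the resistance analysis is contaminated.* Sequencing needs viral RNA, so it is already confined to infected people.
- *That leaving out undiagnosed infected people biases early against late.* Those comparisons are among treated people, and someone the provider does not diagnose receives no study drug.
- *That Sections III and XI plainly define two primary populations.* Section III defines its own influenza-diagnosed term as positive on both tests, and Section XI can be read as shorthand for it, given that it counts confirmed cases. That mismatch is mild. The SAP's ratio is the clearer conflict.

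It can also be said that the diagnosis may draw on the self-test, because Section III places the consultation after it. That might raise p, but no passage makes a positive self-test a condition of the diagnosis. Finally, the p-fold shrinkage is derived for a mean difference. It is not established for the hazard ratios and ordinal models that Section XI plans.

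What stands is that no passage requires a positive PCR for the early-versus-late symptom and viral comparisons, and that the one term which might imply it is undefined.

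**Conclusion.** The concern holds as a defect in how the analysis sets are specified. As written, the early-versus-late comparisons of symptom duration, symptom severity and viral outcomes could include PCR-negative people. Under equal infected shares and no timing effect in the uninfected, a mean difference falls to p times its true value; with unequal shares the bias can go either way. The size cannot be stated as a finding, because p is not in the documents and every value used above is assumed.

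For the primary endpoint, Section XI needs only to repeat Section III. The SAP needs a real correction, since its ratio could not exceed roughly 5% to 8% under the assumptions shown. This is worth correcting before analysis. It does not undermine the Section III primary definition, which already requires laboratory confirmation.

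**What to change.** 1. Use two terms throughout: *telehealth-diagnosed* for operations and *PCR-confirmed* (day 0 Cepheid result) for analysis. Define influenza-positive as PCR-confirmed.
2. State that the early-versus-late comparisons of symptom duration, symptom severity and viral outcomes are run in PCR-confirmed BXM recipients, with all recipients as a supportive analysis. Say how a recipient without a usable day 0 result is classified.
3. Leave the cost analysis in all treated people if preferred, and label it so.
4. Make the primary set in Protocol Section XI and in SAP Section B6, numerator and denominator, identical to Section III.
5. State as a limitation that viral duration cannot be measured in infected people whom the provider did not diagnose, because they give no day 2-3 or day 5-7 swab.

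No new data are needed, and who receives treatment is not affected. The cost is a smaller secondary analysis set, possibly much smaller: at an assumed p of 0.5 to 0.7, the restriction removes 30% to 50% of recipients.
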